#### **10.4 Serious Adverse Event Reporting Period**

All SAEs, whether or not unexpected or considered to be associated with the administration of SB-318, must be reported immediately to Sangamo or its designees by telephone or fax, and must be submitted to Sangamo or its designees on an SAE Report form within 24 hours of the Principal Investigator's discovery of the event. Please refer to the Study Reference Manual for SAE reporting guidelines and contacts.

The reporting period for all SAEs is from subject consenting through the last study visit.

The Principal Investigator is responsible for promptly notifying the IRB/IEC or equivalent in accordance with local regulations of all SAEs. The National Institutes of Health (NIH) requires that all investigators participating in gene transfer research to report all SUSARs. SUSARs will be reported to the appropriate regulatory authorities (FDA/MHRA or equivalent) according to the requirements for expedited safety reporting. Sangamo or its designee will assume the responsibility for reporting SUSARs to the FDA/MHRA or equivalent.

All "serious" events must be followed with appropriate medical management until resolved or stabilized.

#### **10.5 Recording of a Serious Adverse Event**

SAEs reported by telephone must be recorded on a written SAE Report Form provided by Sangamo or its designees. The SAE report form must be submitted to Sangamo or its designees within 24 hours.

The Medical Monitor will then advise the Principal Investigator regarding the nature of any further information or documentation that is required. Follow-up reports must be submitted within 24 hours from the time that the additional information becomes available.

## **10.6 SUSAR Reporting Obligations**

Sangamo or its designee will submit SUSAR reports to appropriate regulatory authorities (including Competent Authorities in all Member States concerned), Ethics Committees, and Principal Investigators as per local laws and regulations. Fatal and life-threatening SUSARs will be submitted no later than 7 calendar days of first knowledge of the event, and follow-up information will be submitted within an additional 8 days. All other SUSARs will be submitted within 15 calendar days of first knowledge of the event.

Principal Investigators are required to report any urgent safety matters to Sangamo or its designee within 24 hours. Sangamo or its designee will inform the regulatory authorities, ethics committees, and Principal Investigators of any events (e.g., change to the safety profile of the study treatment, major safety findings) that may occur during the clinical trial that do not fall within the definition of a SUSAR but may affect the safety of subjects participating in the clinical trials, as required, in accordance with applicable laws and regulations. The reporting period for urgent safety issues is the period from the signing of the ICF through the last study visit.

The Principal Investigator will notify the IRB/IEC or equivalent of SAEs and urgent safety matters, in accordance with IRB/IEC or equivalent requirements and local laws and regulations. A copy of this notification must be provided to Sangamo or its designee.

## **10.7 Pregnancy and Pregnancy of a Partner Reporting**

Pregnancies or pregnancies of partners occurring during this study are to be reported on the Pregnancy Reporting Form. In general, it is expected that pregnancies are reported in the same timeframe as SAEs. Regardless of whether the subject has discontinued participation in the study, the course of all pregnancies and any AEs will be followed to partum at minimum.

## 11. TREATMENT SCHEDULE, DOSE ESCALATION, AND STOPPING RULES

### 11.1 Schedule for Subject Treatment

Subjects who satisfy all eligibility criteria will be enrolled into one of the following treatment cohorts as described below:

Cohort #	Age Range (y)	Total Dose (vg/kg)	# Subjects
1	≥18	1.00E+13	1
2	≥18	5.00E+13	2
3	≥18	1.20E+14	2
4	12-17	TBD	2
5	12-17	TBD	2
6	5-11	TBD	2
7	5-11	TBD	2

For each dose cohort after Cohort 1, two subjects will be dosed  $\geq$  4 weeks apart. SMC review will occur after all subjects in each cohort have  $\geq$  4 weeks of safety data.

The pediatric cohorts will be enrolled only after review of cumulative adult safety data by the SMC (see [Section 12.3](#)). The starting dose for pediatric cohorts 4 through 7 will be decided based on SMC review of study data, and must meet pre-defined safety criteria (see [Pediatric Dosing](#)). Approximately 2 additional subjects may be added to any cohort after SMC review of study data if safety criteria are met (see [Safety Monitoring Committee](#)), with up to a total of 27 subjects in the study.

### 11.2 Dose Escalation Rules

Within each cohort, treatment will be staggered so that each subsequent subject will not be infused until the preceding subject has been observed for at least 4 weeks following administration of SB-318.

Dose escalation to the next cohort will not occur until at least 4 weeks after the last subject in the preceding cohort has been dosed, the safety data from the prior cohort has been reviewed by the SMC, and the SMC has agreed to dose escalate.

Dosing and dose escalation will be paused if a Grade 3 or higher AE occurs, or if two Grade 2 AEs occur within the same organ class and persist for more than 2 weeks with therapy, provided these AEs are not related to the primary MPS I disease or treatment of the MPS I disease. In such an event, the SMC will be convened to assess for potential dose-limiting toxicity (DLT), and to provide recommendations on whether to expand the cohort at the same dose level, to dose de-escalate, or to continue the study as planned (refer to the [Stopping Rules](#)).

### 11.3 Pediatric Dosing

Pediatric dosing will not be initiated until adult safety data has been obtained and reviewed by the SMC, and only after the following conditions have been met:

- $\geq$ 6 months of safety data from 2 adults treated with SB-318 at any dose; and
- $\geq$ 4 weeks of safety data from 2 adults treated with SB-318 at the intended pediatric dose.

Younger pediatric subjects (Cohorts 6 and 7) may not be dosed until older pediatric subjects (Cohorts 4 and 5) have been dosed at the same dose level, and  $\geq 4$  weeks of safety data from each older subject has been reviewed by the SMC.

#### 11.4 ERT Withdrawal

ERT is beneficial but has significant drawbacks, including the need for continuous life-long treatment, development of neutralizing antibodies, lack of efficacy in the brain (due to inability to cross the blood-brain barrier), continued cardiac, musculoskeletal, and upper airway complications, and the inconvenience and cost of weekly IV infusions (Tomanin et al, 2014).

The goal of SB-318 treatment is to abrogate or decrease the need for ERT by using engineered ZFNs to site-specifically integrate a corrective copy of a hIDUA transgene into the genome of the subject's own hepatocytes *in vivo*, resulting in life-long, liver-specific expression of hIDUA.

Subjects who have received SB-318 may no longer require weekly administration of ERT, and may be considered for withdrawal of ERT (if applicable).

ERT withdrawal will be a controlled process, with additional safety monitoring to reduce potential risks to the subject, and is an optional part of the study.

ERT withdrawal may be initiated by the Principal Investigator after consultation with the Sponsor, and only in subjects who are willing and who meet all of the following criteria:

- are  $\geq 12$  weeks post-administration of SB-318;
- are medically stable and can tolerate temporary discontinuation of ERT in the judgement of the Principal Investigator; and
- agree to additional safety monitoring and clinical laboratory tests until the ERT Withdrawal Follow-Up visit (see [Appendix 2](#)).

Study visits associated with ERT withdrawal may occur concurrent with or independent of regular scheduled study visits, but should be combined with regular scheduled study visits whenever possible to reduce study burden. When combined, assessments associated with ERT withdrawal that are duplicated at the regular scheduled study visits should be waived (see [Appendix 1](#)). The ERT Withdrawal Follow-Up visit can occur at any time up to 12 weeks after ERT withdrawal at the discretion of the Principal Investigator.

ERT does not need to be restarted after the ERT Withdrawal Follow-Up visit. However, ERT may be re-initiated at any time based on clinical circumstances or at the judgement of the Principal Investigator.

ERT withdrawal may be repeated if previously unsuccessful. However, ERT withdrawal may not be attempted until at least 12 weeks after ERT has been resumed, and only at the discretion of the Principal Investigator in consultation with the Sponsor. Subjects undergoing repeat ERT withdrawal must be willing and meet the criteria for initial ERT withdrawal listed above.

Documentation of dosing and administration of all ERT should be obtained and recorded on the ERT administration log.

#### 11.5 Study Stopping Rules

The safety data for all subjects within a cohort will be evaluated by the SMC at least 4 weeks after the last subject within that cohort was infused with SB-318. Safety data including AEs and clinical

laboratory test results (chemistry, hematology, etc.) will be evaluated to determine if it is safe to dose escalate.

Subjects in the subsequent cohort may be screened and enrolled prior to the safety review but will not be infused until the SMC has reviewed the data and approved the study for cohort escalation.

The SMC will also be convened to recommend whether the study should be stopped if any of the following criteria are met:

- Any one Grade 3 or higher AE, or any two Grade 2 AEs in the same system organ class that last more than 2 weeks with therapy, provided these AEs are not related to the primary MPS I disease or treatment of the MPS I disease.
- SAE not related to the primary MPS I disease
- Death of a subject.
- Development of a malignancy.

The study may also be stopped for any of the following reasons:

- Sangamo, in consultation with the SMC or Regulatory Agency, decides for any reason that subject safety may be compromised by continuing the study.
- Sangamo decides to discontinue development of SB-318.

If stopping criteria are met, no further dosing of subjects will be performed until a substantial amendment is submitted to the regulatory authority(ies) for review, and the amendment has been approved by the site IRB/IEC or equivalent. When no further enrolling or dosing decisions are required of the SMC, the SMC will no longer meet. Sangamo will review subject safety data on an ongoing basis.

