Stopping Rules	
The SMC will be convened to assess whether changes should be made to the study or whether the study should be stopped if any of the following criteria are met:
 

• Completion of a cohort.

• Any one Grade 3 or higher AE, or any two Grade 2 AEs in the same system organ class that persist for more than 2 weeks with therapy, provided these AEs are not related to the primary MPS I disease or treatment of the MPS I disease.

• SAE not related to the primary MPS I disease.

• Death of a subject.

• Development of a malignancy.

 
The study may also be stopped for any of the following reasons:
 

• Sangamo Therapeutics, Inc. (Sangamo), in consultation with the SMC or Regulatory Agency, decides for any reason that subject safety may be compromised by continuing the study.

• Sangamo decides to discontinue development of SB-318.

 
When no further enrolling or dosing decisions are required of the SMC, the SMC will no longer meet. Sangamo will continue to review subject safety data on an ongoing basis.

Sample Size	
This study will enroll up to a total of 27 subjects (1 subject in Cohort 1 and 2 subjects in each of the other 6 cohorts, with potential enrollment of approximately 2 additional subjects in any cohort). To obtain an evaluable sample size, subjects who prematurely discontinue the study prior to the 12 months of study follow-up (i.e., subjects who were enrolled but not dosed, or were lost to follow-up) may be replaced at the discretion of Sangamo.

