### **12.3 Safety Monitoring Committee**

An external SMC with appropriate medical and scientific expertise will have oversight of the study.

The SMC will be convened after the completion of each cohort to advise whether it is safe to proceed with the next dose cohort, and to provide recommendations on pediatric dosing and expansion of any cohort. The SMC may also be convened at any time if there are excessive or unexpected toxicities associated with the conduct of the protocol. Specifically, the SMC will be convened if the following occurs:

- Any one Grade 3 or higher AE, or any two Grade 2 AEs in the same system organ class that persist for more than 2 weeks with therapy, provided these AEs are not related to the primary MPS I disease or treatment of the MPS I disease.
- SAE not related to the primary MPS I disease
- Death of a subject.
- Development of a malignancy.

The SMC will then evaluate all data to advise whether the changes should be made to the study or whether accrual and dosing should be halted. In addition, no further dosing of subjects will be performed until a substantial amendment is submitted to the regulatory authority(ies) for review, and the amendment has been approved by the site IRB/IEC or equivalent.

The SMC may also recommend changes to the enrollment of cohorts based on cumulative adult and pediatric safety and efficacy data from this and similar ongoing first-in-human clinical trials that are sponsored by Sangamo and that use *in vivo* rAAV2/6-based gene transfer of ZFNs. Specifically, study SB-913-1602 in MPS II subjects uses identical ZFNs (SB-47171 and SB-47898) as the present study in combination with a different donor cDNA (encoding iduronate-2-sulfatase) (Clinicaltrials.gov NCT03041324). Given the similarities of the approaches, relevant data from study SB-913-1602 and other trials sponsored by Sangamo may be shared with the SMC to expand the clinical experience, particularly as it relates to safety and dose, and such data can be used by the SMC to inform its recommendations for the present study.

When no further enrolling or dosing decisions are required of the SMC, the SMC will no longer meet. Sangamo will continue to review subject safety data on an ongoing basis.

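### For the same AE trigger, Protocol 11.2 lets the SMC recommend continuing as planned, while Protocol 12.3 bars further dosing until a substantial amendment, whatever the SMC advises

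*Protocol*

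**What the plan says.** Protocol 11.2 (Dose Escalation Rules) sets the trigger: "Dosing and dose escalation will be paused if a Grade 3 or higher AE occurs", or if two Grade 2 AEs in one organ class persist beyond 2 weeks despite therapy. AEs related to MPS I or its treatment are exempt. The SMC is then convened to look for dose-limiting toxicity. Its other task is "to provide recommendations on whether to expand the cohort at the same dose level, to dose de-escalate, or to continue the study as planned". The sentence ends with a pointer to the Stopping Rules. It mentions no amendment. The Dose Escalation row of the synopsis says the same.

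Protocol 11.5 (Study Stopping Rules) lists the same trigger first among the events that convene the SMC to recommend whether the study should stop: "Any one Grade 3 or higher AE, or any two Grade 2 AEs in the same system organ class that last more than 2 weeks", subject to the same exemption. After a further list of reasons for which the study may be stopped, it adds that, if stopping criteria are met, "no further dosing of subjects will be performed until a substantial amendment is submitted" to the regulator for review and the site IRB/IEC has approved it.

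Protocol 12.3 (Safety Monitoring Committee) lists the same trigger and has the SMC advise on changes or on halting accrual and dosing. The next sentence reads: "In addition, no further dosing of subjects will be performed until a substantial amendment is submitted", again with IRB/IEC approval.

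The Safety Monitoring Committee and Stopping Rules rows of the synopsis, and SAP section 10, repeat the trigger and contain no amendment step.

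**The concern.** This rule governs what happens after a serious safety signal in a staggered, dose-escalating study of a single infusion that, as Protocol 12.1 notes, cannot be reversed. The protocol should give one answer to the question of what has to happen before the next subject is infused. It gives two. In 11.2, an SMC recommendation is the only step named, and that recommendation may be to change nothing. In 12.3, the recommendation is not enough: a regulatory submission and an ethics approval must follow whatever the SMC says.

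If the SMC recommended continuing and dosing resumed on that basis, the sponsor would have followed 11.2 and breached 12.3. If the sponsor waited for an amendment, the option to continue as planned in 11.2 would have had no effect on dosing. Recommending no change also sits oddly with a mandatory amendment, because there would be no change of plan to amend.

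**Working it through.** No arithmetic applies: the plan states no figure for this rule. The check sets the provisions for the shared trigger side by side.

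| Place | Role of the SMC after the trigger | Amendment before further dosing? | Condition attached to the bar |
|---|---|---|---|
| Protocol 11.2; synopsis, Dose Escalation | Recommends expansion, de-escalation or no change | Not mentioned | None stated |
| Protocol 11.5 | Recommends whether to stop | Yes | Only if stopping criteria are met; term not defined |
| Protocol 12.3 | Advises on changes or a halt | Yes | None; added to the advice |
| Synopsis, Safety Monitoring Committee and Stopping Rules | Determines or assesses changes, or a halt or stop | Not mentioned | None stated |
| SAP section 10 | Convened | Not mentioned | None stated |

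1. **Is it the same trigger?** Yes. Grade, number of events, duration and exemption agree in 11.2, 11.5 and 12.3, apart from trivial wording such as last versus persist. Sections 11.5 and 12.3 also list certain SAEs, deaths and malignancies, which 11.2 does not, so the direct conflict with 11.2 concerns the shared AE trigger.

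2. **What does 11.5 require?** It has two possible readings.
   - Reading A: stopping criteria are the listed triggers. The list is introduced as criteria that may be met, and the later sentence speaks again of criteria being met. On this reading every trigger brings the amendment bar, and 11.5 conflicts with 11.2.
   - Reading B: the bar applies only once the SMC has recommended stopping. The sentence is conditional, and the list serves to convene the SMC. On this reading 11.5 fits 11.2.

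3. **Suppose the SMC recommends continuing as planned.**
   - Under 11.2, dosing may resume.
   - Under 11.5, it is barred on reading A and not barred on reading B.
   - Under 12.3, it is barred, because the sentence is additional to the advice and does not depend on it.

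4. **Does any reading of 11.5 remove the conflict?** No. Reading B reconciles 11.5 with 11.2 but leaves 12.3 untouched. Reading A puts both 11.5 and 12.3 against 11.2.

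5. **What exactly does the bar demand?** Submission to the regulator for review, and approval by the site IRB/IEC. The text does not require regulatory approval.

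**The case against.** The strongest reply is that the sections form one sequence: pause, SMC review, and an amendment only if the study is stopped. Section 11.2 points to the Stopping Rules, 11.5 is expressly conditional, and the sentence in 12.3 comes straight after the reference to halting accrual and dosing, so it may have been meant to apply only to a halt. As an account of intent this is plausible, and for 11.5 it stands. For 12.3 it does not: the sentence opens as an addition and carries no condition, so a reader has to supply the limit. The pointer in 11.2 leads to 11.5, where the key term is undefined.

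Four stronger readings are tempting, and the documents do not support them.

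- A reader might infer that sites could act in opposite ways on the same event. The trigger stops dosing under 11.2 as well as under the amendment bar, and one SMC advises the sponsor. The dispute is only about restart.
- A reader might infer that the amendment bar would hit most runs of the trial. The documents give no rate of qualifying AEs. At an assumed 5% per subject, with independence, the chance of at least one among the 13 planned subjects (1 + 6 × 2) is 1 − 0.95^13 = 0.487. The claim therefore turns on the assumed rate, and it also presupposes that every trigger requires an amendment.
- The entry "Completion of a cohort" in the synopsis Stopping Rules might look like a routine event treated as a stopping event. That list only convenes the SMC, and the synopsis attaches no halt to it.
- The exemption, "provided these AEs are not related to the primary MPS I disease or treatment of the MPS I disease", might be read to cover events caused by SB-318. The protocol calls SB-318 the study treatment or investigational product and names HSCT and ERT as current therapies. Serious SB-318-related events reach the SMC through the separate SAE criterion, which has no treatment exemption.

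**Conclusion.** The concern holds in a bounded form. Protocol 11.2 and 12.3 cannot both be followed as written when the SMC recommends continuing after a qualifying AE. Protocol 11.5 is ambiguous rather than contradictory, and the synopsis and SAP section 10 omit the amendment step altogether.

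The size is qualitative: the condition for resuming dosing is undetermined at every qualifying event that occurs while doses remain to be given. This conclusion rests on the wording alone and needs no assumption about AE rates. It does not depend on which reading of 11.5 is adopted, and it takes no position on which rule is clinically right.

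**What to change.** Reconcile the Dose Escalation, Safety Monitoring Committee and Stopping Rules rows of the synopsis with Protocol 11.2, 11.5 and 12.3, so that all six places give one sequence in identical words. The sequence should state which outcomes of SMC review allow dosing to resume on the SMC's recommendation and which require a substantial amendment first.

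Define stopping criteria in 11.5, so that it is clear whether the term means that a listed trigger has occurred or that the SMC has recommended stopping. Make the status of the amendment sentence in 12.3 agree with that definition. Which rule applies to which outcome is for the sponsor to decide. SAP section 10 can then refer to the reconciled text.

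The cost is wording in a protocol amendment. Sample size, data collection and the planned analyses do not change.

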## **12 SUBJECT WITHDRAWAL/DISCONTINUATION, AND SAFETY MONITORING COMMITTEE**

### **12.1 Subject Withdrawal and Discontinuation from Study**

Subjects may withdraw or should be discontinued from study for any of the following reasons:

- Request by the subject to withdraw.
- Request of Sangamo or primary care provider if he or she thinks the study is no longer in the best interest of the subject.
- Pregnancy prior to SB-318 infusion.
- Subject judged by the Principal Investigator to be at significant risk of failing to comply with the provisions of the protocol as to cause harm to self or seriously interfere with the validity of the study results.
- At the discretion of the IRB/IEC or equivalent, Office for Human Research (OHR), regulatory authority (e.g., FDA/MHRA or equivalent), Principal Investigator, or Sangamo.

Subjects will be strongly encouraged to continue and comply with follow-up safety evaluations. If a subject withdraws consent or discontinues from the study post-study treatment, a conference between the Principal Investigator and Medical Monitor will take place to ensure that the subject understands the importance of the study follow-up and that the study treatment cannot be reversed even if a subject drops out of the study follow-up. If the subject agrees, a reduced follow-up testing schedule may be arranged including telephone call and safety labs to assess treatment-related AEs and disease status.

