#### **10.2 Adverse Event Reporting Period**

AEs will be monitored continuously during the study from the time that the subject has provided written informed consent through the subject's last day of study participation. Subjects will be queried and events will be assessed at each clinic visit. A treatment-emergent AE (TEAE) is any AE with an onset from any time from administration of the study treatment through the last study visit, whether or not it is considered causally related to the study treatment.

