### **13.4 Primary Endpoint**

The primary endpoint of this study is the incidence of treatment-emergent AEs (including SAEs). Additional safety evaluations will include:

- Routine hematology, chemistry, and liver function laboratory tests, vital signs, physical exam, ECG, ECHO, and concomitant medications.
- Monitoring of chimerism in post-HSCT subjects.
- Cranial nerve exam and muscle strength testing.
- Serial AFP testing and MRI of liver to evaluate for liver mass.

Safety assessment will be performed on all subjects. All reported AEs will be coded to a standard set of terms using the Medical Dictionary for Regulatory Activities (MedDRA).

Treatment-emergent adverse events will be summarized overall and by treatment cohort. For each subject, the maximum reported severity of each adverse event will be used in the summaries by severity grade. In addition, all serious adverse events and AEs related to study treatment will be summarized.

Laboratory data will be summarized for each time-point at which specimens are collected. Change-from-Baseline values may be calculated for selected laboratory parameters. Shift-tables (Change-from-Baseline relative to the normal range) may be constructed for selected laboratory parameters.

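### After a dosed subject leaves the study, Protocol 12.1 directs follow-up at treatment-related AEs, while the primary endpoint counts TEAEs of any cause

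*Protocol*

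**What the plan says.** **Leaving the study.** Protocol 12.1 introduces its list with "Subjects may withdraw or should be discontinued from study for any of the following reasons". One ground is tied to the time before dosing: "Pregnancy prior to SB-318 infusion". The others are not. They are the subject's own request; a best-interest request from the sponsor or primary care provider; the discretion of the ethics committee, regulator, investigator or sponsor; and "Subject judged by the Principal Investigator to be at significant risk of failing to comply with the provisions of the protocol". That last ground is qualified: the risk must be such as to harm the subject or seriously compromise the validity of the results.

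Dosed subjects are in scope, because the section goes on to the case "If a subject withdraws consent or discontinues from the study post-study treatment" and calls for a conference between the investigator and the medical monitor. It also says: "Subjects will be strongly encouraged to continue and comply with follow-up safety evaluations". For a subject who agrees, "a reduced follow-up testing schedule may be arranged including telephone call and safety labs to assess treatment-related AEs and disease status".

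**What is counted.** Protocol 13.4 makes the incidence of TEAEs, SAEs included, the primary endpoint. Protocol 10.2 counts a TEAE from dosing to the last study visit, "whether or not it is considered causally related to the study treatment", and SAP 8.1.1 does the same. Protocol 10.4 requires every SAE to be reported over the same closing window, whatever its association with SB-318. The safety committee triggers in Protocol 11.5 and 12.3 set aside events due to MPS I or, for the graded AEs, its treatment. They do not require a link to SB-318.

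**The concern.** SB-318 is a single infusion, and 12.1 itself notes that it cannot be undone. Taking a dosed subject off study therefore removes no exposure; it ends or thins observation. The only AE purpose that 12.1 gives for what follows is narrower than the endpoint. Relatedness is decided by the investigator (Protocol 10.3) in an open-label study (3.1).

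At stake are later events whose link to the product is not recognised at first. Protocol 8.1.3 names tumour formation as a risk, and 6.9 schedules AFP and liver MRI through Month 36 for that reason. While dosing decisions are still being made, the safety committee also depends on hearing of deaths, malignancies, SAEs and Grade 3 or higher AEs without a prior judgement that SB-318 caused them.

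The protocol can carry AE follow-up past discontinuation when it chooses to: 10.7 follows pregnancies, with any AEs, whether or not the subject has left the study. AEs in general have no such provision.

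**Working it through.** **1. The passages side by side**

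| Place | Which events | Until when |
|---|---|---|
| Protocol 10.2, 13.4; SAP 8.1.1 (TEAEs) | Any cause | Last study visit |
| Protocol 10.4 (SAEs) | Any cause | Last study visit |
| Protocol 6.10 (Early Termination visit) | AE assessment, no causality filter | Exit |
| Protocol 12.1 (reduced schedule) | Stated aim: related AEs, plus disease status | Not stated |

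Neither document says whether a reduced-schedule contact is a study visit. That leaves two readings.
- *It is not a study visit.* The TEAE and SAE windows close at exit, and no later event counts, related or not.
- *It is a study visit.* Protocol 10.2 to 10.4 would call for all AEs and SAEs, but 12.1 tells staff that the purpose of the contact is related ones. The two instructions conflict.

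**2. Direction**

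All subjects who receive any infusion stay in the analysis (Protocol 13; SAP 4.2.2 and 8), and SAP 4 imputes nothing unless otherwise specified. SAP 8.1.1 names an undefined intent-to-treat set as its percentage base, but the AE table shells use the Safety Set. Crude incidence is subjects with the event divided by dosed subjects, so an unseen event counts as no event. The bias can only be downward. It arises only for event types that the subject had not already had before exit.

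**3. Scale of one subject**

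The enrolment figure reproduces: 1 + 2 × 6 = 13 planned; 13 + 2 × 7 = 27 maximum (Protocol 13.1). One subject's share is 100/n points:
- n = 1: 100 points
- n = 2: 50 points
- n = 13: 7.7 points
- n = 27: 3.7 points

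Share of the 36-month window lost by leaving at month t is (36 − t)/36: 92% at month 3, 67% at month 12, 33% at month 24.

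**4. Illustrations on assumed rates (none is in the documents)**

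*Collection stops at exit.* With a constant hazard and 36-month risk p for an event type, the part seen by month t is 1 − (1 − p)^(t/36). For exit at month 12:

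| Assumed p | Seen | Missed (points) |
|---|---|---|
| 10% | 3.5% | 6.5 |
| 30% | 11.2% | 18.8 |
| 50% | 20.6% | 29.4 |
| 80% | 41.5% | 38.5 |

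These are per leaver. In a cohort of 2 with one leaver and p = 50%, the expected shortfall in cohort incidence is 29.4/2 = 14.7 points.

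*Only related events are recorded.* Suppose the leaver has a Poisson number of further AEs with mean 1, and a share u is called unrelated. The chance of recording any AE falls from 1 − e^(−1) = 63% to 1 − e^(−(1−u)): 50% for u = 0.3, 33% for u = 0.6, 10% for u = 0.9. This is the extreme case in which the stated aim is applied as a strict filter.

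**The case against.** The strongest reply is that 12.1 forbids nothing. The schedule may be arranged, needs the subject's agreement, and also covers safety labs and disease status. Protocol 10.3 makes a Grade 3 or 4 laboratory worsening from Baseline reportable without any test of relatedness, unless a reported diagnosis already covers it. The Early Termination visit asks every leaver back for unfiltered AE assessment, liver panel, AFP, liver MRI and neurological examination. The compliance ground is qualified, and reduced follow-up is unavoidable where consent is withdrawn. Subjects may move to the long-term follow-up study after 12 months, so nobody is guaranteed 36 months in this one. The study is descriptive.

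All of this stands, and it confines the point to the time after the Early Termination visit. It also rules out some stronger conclusions a reader might draw:
- *That capture of unrelated events drops to zero by rule.* No such rule exists.
- *That the share of events called related must be inflated.* If the contacts are not study visits, no later event of either kind is counted. If they are, 10.2 to 10.4 still ask for all events. Inflation needs the contacts to count and staff to record only related events; the documents do not establish that.
- *That subjects must be removed for likely non-compliance.* This drops the qualifier about harm and validity.

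Replacement of subjects who leave before 12 months (Protocol 13.1) restores the head count. It does not recover a dosed leaver's unobserved time. Encouragement to continue does not settle what is recorded or counted afterwards.

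**Conclusion.** The mismatch is real but limited. Before and at the Early Termination visit, AEs are collected for all causes. After it, Protocol 12.1 states an AE purpose narrower than the primary endpoint, SAE reporting and the safety committee triggers, and neither document says whether these contacts fall inside the TEAE window. All-cause ascertainment then either ends or is directed at events that the open-label investigator judges related. Any resulting bias in crude incidence is downward.

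The size cannot be computed, because no dropout or AE rate is given. The firm figures are the 50 or 100 percentage points that one subject represents in a planned cohort of 2 or 1; the other illustrations rest on assumed hazards, AE counts and relatedness shares. The avoidable part concerns dosed subjects who still consent and are taken off by the investigator or sponsor. A correction of wording is enough; the design need not change.

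**What to change.** 1. In Protocol 12.1, replace *treatment-related AEs* with *all AEs and SAEs regardless of relationship*. Keep disease status.
2. In Protocol 10.2 and SAP 8.1.1, state that reduced-schedule contacts count as study visits for the TEAE window. Carry the same meaning of last study visit into the SAE period in 10.4.
3. In 12.1, state that a dosed subject who is taken off protocol procedures by the investigator or sponsor, and who still consents, is offered this reduced safety follow-up. Leave the existing harm-to-self and best-interest grounds for stopping procedures as they are. A closed list of post-infusion exit grounds would go further and would remove those protections, so it is not proposed here.

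The cost is amended wording in two documents, a few more AE entries per contact, and acceptance of less complete data from these subjects than scheduled visits would give. Subjects who withdraw consent and decline further contact remain unobserved under any wording.
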